Suvorexant for Opioid/Stimulant Co-use

NCT05546515

9/19/2024

JHM IRB - eForm A – Protocol

- Use the section headings to write the JHM IRB eForm A, inserting the appropriate material in each. If a section is not applicable, leave heading in and insert N/A.
- When submitting JHM IRB eForm A (new or revised), enter the date submitted to the field at the top of JHM IRB eForm A.

1. Abstract

The opioid epidemic has led to an unprecedented rise in opioid use disorder (OUD) cases and overdose deaths. In recent years, these increases have been accompanied by a rise in opioid/stimulant co-use, an issue that has existed for decades and for which no effective treatment has ever been identified. Current increases in opioid overdose deaths are now largely driven by stimulant co-use. Thus, innovative treatments that are safe and effective among patients co-using opioids and stimulants are urgently needed. Suvorexant (SUVO) is an FDA-approved medication used to treat insomnia. SUVO interacts with the brains reward system in such a way that it may reduce craving for stimulants in persons using opioids, and we recently also found that SUVO reduced craving and increased total sleep time among individuals who were withdrawing from opioids. That study also showed that SUVO was extremely safe and well-tolerated in persons using opioids.

This between-subjects, double-blinded, randomized controlled pilot study will recruit patients who are receiving methadone or buprenorphine treatment for OUD and are using cocaine. Participants will be randomly assigned to receive 28-30-days of SUVO or placebo. They will visit the clinic regularly to provide urine drug screens and complete questionnaires and will wear a device that can measure their sleep parameters. We expect that relative to persons who receive placebo, individuals who receive SUVO will 1) be less likely to screen positive for cocaine and/or opioids on urine drug screens, 2) will report lower drug craving, 3) will have better sleep continuity (i.e., longer total sleep time, shorter wake after sleep onset, and greater self-reported sleep quality, and 4) will report overall lower stress and better mood than persons who receive placebo. We also expect that patients will not have side effects from SUVO. These preliminary data will inform whether this FDA-approved medication may help patients stop co-using opioids and stimulants, which can be scaled up to reduce public health consequences related to co-use.

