2. Objectives (include all primary and secondary objectives)

Primary Aim 1. Examine whether individuals who are randomly assigned to SUVO 20mg (oral) will be less likely to test positive for (i) cocaine and (ii) non-prescribed opioids on urine drug screens (UDS) and will self-report lower opioid and cocaine craving, relative to those receiving placebo.

Date: 09/19/2024

Principal Investigator: [name].

Application Number: IRB00341328

Secondary Aim 1. Examine whether, relative to placebo, SUVO 20mg will improve self-reported sleep quality and total sleep time, as assessed via a sleep diary and an actigraph-like device, and will reduce self-reported insomnia symptoms and wake after sleep onset (WASO).

Secondary Aim 2. Given previous work suggesting that Suvorexant has a good safety profile among patients using opioids and patients using cocaine, a secondary aim will test no between-group differences in the rate of adverse events between individuals assigned to Suvorexant and placebo.

Secondary Aim 3. Examine whether SUVO 20mg will be associated with lower stress reactivity, lower self-reported stress and negative affect, and greater positive affect, relative to placebo.

3. Background (briefly describe pre-clinical and clinical data, current experience with procedures, drug or device, and any other relevant information to justify the research)

Opioid/stimulant co-use is a public health crisis that is increasing in prevalence (Goodwin et al., 2021) and directly contributing to increases in overdose deaths and disproportionately impacting minority individuals (Townsend et al., 2022). Individuals engaged in opioid/stimulant co-use face a greater risk of treatment discontinuation and continued substance use (Levin et al., 2015).

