Chronic opioid exposure can produce supersensitivity in dopamine neurons that could (theoretically) increase the reinforcing effects of cocaine in persons with OUD (Strickland et al., 2022). This testable theory may explain why new onset stimulant use develops in persons who are receiving opioid agonist treatment of OUD, a trend that has been observed for decades but for which no effective treatment has ever been identified. The following proof-of-concept study will examine whether antagonizing the orexin system with suvorexant (SUVO) will reduce cocaine co-use in persons receiving methadone or buprenorphine treatment. SUVO is an FDA-approved medication for treatment of insomnia, that has also shown substantial promise in reducing opioid craving and withdrawal symptoms.

This approach is supported by preclinical evidence that orexin antagonism blocks morphine sensitization of the ventral tegmental area (Mazaheri et al., 2022) and interacts meaningfully with the reward pathway and may have both direct effects on cocaine use and indirect effects by way of reducing opioid sensitization (Aston-Jones et al., 2010). This is also supported by our Phase II study that showed SUVO 20mg produced significant and clinically-meaningful reductions in opioid craving, insomnia, and withdrawal in persons withdrawing from opioids, a good safety profile, no evidence of abuse potential, and no SUVO discontinuation symptoms (Huhn et al., 2022). Further support suggested that SUVO improved restful sleep and reduced wake after sleep onset among patients using cocaine (Suchting et al., 2020). Additionally, SUVO has an excellent safety profile; previous studies examining SUVO in populations who use substances reported no serious adverse events (Huhn et al., in press; Suchting et al., 2020). SUVO also has also been shown to have low abuse liability (Herring et al., 2016; Huhn et al., 2022), and does not produce withdrawal symptoms after discontinuation (Herring et al., 2016).

4. Study Procedures

- a. Study design, including the sequence and timing of study procedures (distinguish research procedures from those that are part of routine care).

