Screening visit(s). Screening procedures may be scheduled across more than 1 day to meet participant schedules. Prior to completing any study-related screening, participants will review and sign an informed consent form with a trained staff member. Participants will be given the opportunity to do an in-person or a remote consent. For participants that complete the remote consent, some screening procedures will also be completed remotely, including interviews and questionnaires. Participants who complete this initial eligibility screening will complete the remainder of their screening visit in person. During the screening visit, participants will be assessed for inclusion and exclusion criteria. A urine drug-screen will be collected to assess for recent drug exposure and pregnancy (when indicated), the Mini-International Neuropsychiatric Interview (M.I.N.I.), the Addiction Severity Index (McLellan, Cacciola, & Zanis, 1997), the Columbia Suicide Severity Rating Scale, a demographic questionnaire, and a health form assessing current conditions and medications will be used to help evaluate participant eligibility.

Baseline/Randomization visit. Following determination of eligibility, participants will be randomized (stratified by gender) to receive 20mg of SUVO (the maximum FDA approved dose) or placebo. Randomization will occur prior to visit 1. At the randomization visit, participants will provide a urine sample that will be tested for recent drug use and complete self-report measures as described below. They may also complete a cue-induced craving paradigm, a probabilistic reward task, and the Trier Social Stress Test (TSST) described below. Participants will also be provided with an actigraph-like device to wear for the duration of their study participation to assess sleep.

Medication dispensing will begin during the baseline session. Participants will receive a blister package with 7-days of medication dispensed as two capsules (10mg SUVO or placebo) so that medication doses can be reduced to 50% of the dose if requested by a

Date: 09/19/2024

Principal Investigator: [name].

Application Number: IRB00341328

participant. Participants will also receive a 3-day blister package as a contingency strategy in case of missed visits. Participants will be instructed to return blister packages once weekly as a measure of medication compliance.

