Secondary Aim 1 and 3. To examine whether SUVO 20 mg improves 1) insomnia symptoms, 2) indices of sleep continuity, and 3) co-occurring affective symptoms relative to placebo, a series of mixed effects models will be conducted. For each model, we will include main effects of timepoint and medication group, as well as an interaction term. If the two treatment groups are systematically different on demographic or use characteristics at baseline, these measures will be included as covariates in the analysis. Models will involve a random intercept. Mixed effects models will also be used to compare drug cue reactivity at baseline and during the final week.

Secondary Aim 2. To compare SUVO 20mg to placebo on number of adverse events experienced, t-tests will be used.

Power analysis and sample size. A sample size of 40 will be used in this study. For all aims, we are sufficiently powered to detect moderate-to-strong effect, which has been observed in

Date: 09/19/2024

Principal Investigator: [name].

Application Number: IRB00341328

previous studies (e.g., Huhn et al., 2022). Due to our smaller sample size, effect size measures will also be considered.

All analyses will be conducted in SPSS and R. Two-tailed tests and an alpha level of .05 will be used.

d. Early stopping rules.

Participants will discontinue the study if the medical team determines it is not safe to continue in the study or if they request to discharge from the study. Additional stopping rules will include not abiding by study policies and procedures, or engaging in behaviors towards staff or other participants that are abusive. Finally, development of an intercurrent illness or condition that changes the participant's risk profile may result in a medically-related discharge from the study.

8. Risks

a. Medical risks, listing all procedures, their major and minor risks and expected frequency.

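### The claim that 40 participants give sufficient power for all aims fails for the adverse-event t-test at a moderate effect (about 34% power) and is unsupported for the mixed-model aims

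*Combined protocol and SAP*

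**What the plan says.** The sample size paragraph in section 7c of the protocol states "A sample size of 40 will be used in this study", followed by "For all aims, we are sufficiently powered to detect moderate-to-strong effect". It supports this by pointing to effects seen in earlier studies, and adds that effect size measures will also be considered because the sample is small. The testing rule is "Two-tailed tests and an alpha level of .05 will be used".

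The same section assigns the analysis for Secondary Aim 2: "To compare SUVO 20mg to placebo on number of adverse events experienced, t-tests will be used". Section 2 frames that aim as one where "a secondary aim will test no between-group differences in the rate of adverse events", and the abstract says "We also expect that patients will not have side effects from SUVO".

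Section 4a describes allocation only as "participants will be randomized (stratified by gender) to receive 20mg of SUVO" or placebo, without a ratio. No section gives a numerical effect size, a standard deviation, an adverse-event rate, a target power or an expected dropout, although section 4g lists grounds for removing participants.

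**The concern.** The power statement has no exceptions, so it covers the adverse-event comparison. That comparison is one between-group t-test with one value per participant. It gains nothing from the repeated visits that help the craving, urine and sleep outcomes, and about 20 per arm is few for such a test.

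The support offered does not reach this aim. Section 3 describes the earlier study's findings as "SUVO 20mg produced significant and clinically-meaningful reductions in opioid craving, insomnia, and withdrawal in persons withdrawing from opioids, a good safety profile". The effects named there concern craving, insomnia and withdrawal. Safety is given only as a favourable description, so the documents contain no adverse-event effect to which the power statement could refer.

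For most aims, low power works against the sponsor's hypothesis. Here it works in its favour. The aim expects no difference and the plan sets no margin for how small a difference would count as none. A non-significant t-test could therefore be taken as confirmation, from a test that the protocol itself calls sufficiently powered.

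**Working it through.** **Reproducing the plan's figure.** This is not possible. The total of 40 is stated, but no effect size or power is given from which to derive it. Working backwards, 20 per arm gives 80% power at d=0.91 two-sided. A one-sided 0.05 test gives 79.9% at d=0.8, but section 7c specifies two-tailed tests, and the one-sided power at d=0.5 is only 46%.

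**Inputs from the protocol (section 7c).** Total 40; two-sided alpha 0.05; t-test on the number of adverse events.

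**Assumptions.** Equal arms of 20, which is the most favourable split; no dropout; moderate d=0.5 and strong d=0.8; 80% as sufficient power. Other allocations and losses are shown below.

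**Power formula.** Noncentral t with df = n1 + n2 − 2 and noncentrality d / √(1/n1 + 1/n2). For 20 v 20, √(1/20 + 1/20) = 0.316, df = 38 and the critical t is 2.024.
- d=0.5: noncentrality 0.5/0.316 = 1.58, power 33.8%
- d=0.65: noncentrality 0.65/0.316 = 2.06, power 51.7%
- d=0.8: noncentrality 0.8/0.316 = 2.53, power 69.3%

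| Arms | d=0.5 | d=0.65 | d=0.8 | d detectable at 80% |
|---|---|---|---|---|
| 20 v 20 | 34% | 52% | 69% | 0.91 |
| 22 v 18 | 34% | 51% | 69% | 0.91 |
| 24 v 16 | 33% | 50% | 68% | 0.93 |
| 18 v 18 (10% loss assumed) | 31% | 47% | 65% | 0.96 |
| 16 v 16 (20% loss assumed) | 28% | 43% | 59% | 1.02 |

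The smallest equal arms that give 80% power are 64 at d=0.5, 39 at d=0.65 and 26 at d=0.8.

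**Count data.** Adverse events are counts, so the t-test was also simulated: 20 per arm, 40,000 trials per setting, placebo mean 0.5 to 2 events (assumed), and d defined as the difference divided by the root of the mean variance.

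| Assumed variance | d=0.5 | d=0.8 |
|---|---|---|
| Poisson (variance = mean) | about 34% | about 70% |
| mean + mean² | about 33% | about 77% |
| mean + 2·mean² | about 32% | about 86% |

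The result at d=0.5 hardly moves. The result at d=0.8 depends on the dispersion and passes 80% in the most dispersed case. That case is extreme, because d=0.8 then means roughly six times as many events or more on active drug as on placebo.

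**What a null result would show.** The 95% CI half-width in SD units is t(0.975, n1 + n2 − 2) × √(1/n1 + 1/n2). For 20 v 20 this is 2.024 × 0.316 = 0.64. For 16 v 16 it is 2.042 × 0.354 = 0.72. Both exceed 0.5, so an observed difference of zero would still be compatible with a moderate difference in either direction.

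**Repeated outcomes, for contrast.** Averaging m visits with within-person correlation ρ multiplies the variance by (1 + (m − 1)ρ)/m. For 8 visits and an assumed ρ of 0.3, 0.5 or 0.7, power is 70%, 54% or 43% at d=0.5, and 98%, 91% or 82% at d=0.8. This simple average is not the group-by-time test in the plan. It shows only that the answer depends on a correlation that the protocol does not give.

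**The case against.** The strongest reply is that no stated number is wrong. The effect range, the 80% target and the equal split all come from outside the protocol, and a strong effect has no upper limit: at d of about 0.91 or more the t-test does reach 80%. This stands in part. The point is not a miscalculated figure, and the shortfall at the strong end depends on convention and on how dispersed the counts are. It does not rescue the moderate end, which the statement also covers and which fails in every allocation, loss and count setting tried.

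A second reply is that expectations are modest. The abstract calls the trial a pilot, section 3 calls it proof-of-concept, section 6c says it is not meant to go to the regulator as a well-controlled study, and section 8b has adverse events reported to the study team daily and discussed at least weekly. These limit the harm and protect participants. None of them withdraws the power statement, and considering effect sizes as well does not say how a null adverse-event result will be read.

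A reader might infer three stronger things that the documents do not support. First, that the trial is underpowered for every aim: repeated visits may well give 80% power for strong effects, so the mixed-model claim is only unsupported. Second, that no strong adverse-event difference could be detected: the count results show otherwise for some dispersions. Third, that the sponsor plans to present a non-significant test as proof of safety: no section says so. The wording merely leaves that reading open.

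**Conclusion.** The universal power statement is wrong as written. Under the stated assumptions it fails for Secondary Aim 2 at a moderate effect: about 34% power with 20 per arm, 28% with 16 per arm, and 32% to 34% for simulated counts. At d=0.8 power is 69% for roughly normal data and about 70% to 86% for skewed counts, so the strong end should be described as dependent on assumptions. For the mixed-model outcomes the claim lacks the inputs needed to judge it. The consequence is confined to interpretation: a no-difference aim with no margin, tested with an interval of about ±0.64 SD, cannot support a conclusion of equal adverse-event burden. This should be fixed, and wording is enough.

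**What to change.** In section 7c, remove the extension of the power claim to all aims. State that this is a pilot of 40 participants and give the allocation ratio. If it is 1:1, state that a single between-group t-test with 20 per arm has 80% power only for d of about 0.91 (roughly normal data, no dropout), and is not powered for a moderate effect. For the mixed-model aims, either give the detectable effect for the planned test with its assumed correlation, number of visits and dropout, or make no power claim.

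In section 2, reword Secondary Aim 2 as estimating the between-group difference in adverse events, so that it agrees with the revised statement. In section 7c, report that difference with a 95% confidence interval and say that a non-significant test will not be read as evidence of no difference.

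No participants, visits or tests are added. The cost is a less favourable stated sensitivity and a weaker permitted safety conclusion.

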Weekly visits. Participants will complete visits twice weekly during the study period. At these visits, participants will be asked to complete a urine drug screen and self-report measures as described below. Medication will be dispensed once weekly during these visits.

Final/Exit visit. The final study visit will be collected at day 28-30 (+7 days) or the final day of study participation. At their final visit, participants will complete a urine drug screen and self-report measures, and tasks. Participants will be able to request SUVO prescriptions from their provider if desired and all participants can request study drug unblinding after data collection is closed.

Follow-up phone visit: Participants will be contacted via phone after the final/exit visit. Information will be collected on their experience during the study, any changes in symptoms following study exit, treatment plans going forward, and other feedback regarding the study.

Sleep diaries: To facilitate scoring of actigraphy data, participants will be asked to complete nightly sleep diaries.

The following study Measures may be used:

- Mini-International Neuropsychiatric Interview (M.I.N.I.): The MINI is a semi-structured interview that will be used to assess presence of stimulant use disorder.
- Addiction Severity Index: The ASI will be used to collect information related to severity of recent substance use disorder
- Columbia Suicide Severity Rating Scale: The C-SSRS is the standard for assessing present risk for suicidality. It will be administered at screening and end of study, and point prevalence during the study as indicated.
- Demographic questionnaire. This will ask participants basic demographic information (e.g., gender, age, race, ethnicity, employment status, etc.)
- Medical History: A self-reported medical history will be collected to determine eligibility for suvorexant administration.
- Assessment of previous medication administration: Participants will be asked whether they have ever received a number of different medications, either illicitly or through a prescription.
- Medication expectancy questionnaire. Participants will be asked to rate how much they expect to like the study drug, as well as how much they expect the study drug to help improve various symptoms (i.e., opioid use, cocaine use, sleep, stress).

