We are proposing to administer SUVO 20mg, which is an FDA-approved dose. We are not requiring insomnia as an inclusion criterion in order to focus more specifically on opioid-stimulant co-use behaviors. We have collected substantial evidence that SUVO is safe and does not increase risk of misuse in persons with OUD (see Huhn et al., 2022).

- c. Justification and safety information if non-FDA approved drugs without an IND will be administered.

SUVO is an FDA-approved medication. We are not submitting for an IND because the intervention is not intended to be reported to the FDA as a well-controlled study or for a significant label change, it is not intended to support a significant change in the advertising for the product, and it does not involve a route or dose level or patient population for which there is increased risk associated with use of the drug.

7. Study Statistics

- a. Primary outcome variable

Urine drug-screen results. Participants will complete a urine drug screen at each clinic visit. The presence or absence of non-prescribed opioids and/or cocaine will be recoded at twice-weekly sessions. The primary outcomes will be 1) the presence of absence of opioids at each screen, 2) the presence or absence of cocaine at each screen, and 3) the presence or absence of a screen that is negative for all illicit substances.

Self-reported opioid and cocaine craving. Participant will complete visual analogue scale measures of opioid and cocaine craving during each weekly visit. The average score across each visual analogue scale will be a primary outcome.

Opioid and cocaine cue reactivity. Participants will also complete visual analogue scales in the presence of drug cues. Average scores on visual analogue scales will serve as a primary outcome

- b. Secondary outcome variables.

Insomnia Severity Index Scores. The Insomnia Severity Index is a seven-item screening measure of insomnia. Items are rated on a five-point scale. A cut score of 15 is typically used to demarcate clinical insomnia. The scale has been shown to have excellent psychometric properties, including among patients with substance use disorders.

Sleep Continuity. Using actigraphy and sleep-diaries (in which persons will be asked to report on their sleep the night before the assessment), we will focus on three commonly used sleep continuity outcomes: 1) total sleep time (TST), or the total number of minutes that an individual

Date: 09/19/2024

Principal Investigator: [name].

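### Six or seven outcomes are labelled primary and each is tested at .05, with no lead outcome, no deciding model term and no rule for mixed results; the primary set also differs between sections

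*Combined protocol and SAP*

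**What the plan says.** Section 7a lists the primary outcomes in three groups.

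- **Urine screens.** "The primary outcomes will be 1) the presence of absence of opioids at each screen", then the same for cocaine, then "the presence or absence of a screen that is negative for all illicit substances". That is three outcomes.
- **Craving.** For the opioid and cocaine scales, "The average score across each visual analogue scale will be a primary outcome". The wording treats each scale separately, so this is two outcomes.
- **Cue reactivity.** "Participants will also complete visual analogue scales in the presence of drug cues", and "Average scores on visual analogue scales will serve as a primary outcome". This is one outcome if opioid and cocaine cues are pooled, two if not.

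Section 7c (Primary Aim 1) analyses these in a series of mixed models. Each has timepoint, group and their interaction. Section 7c closes with a single error rate for all analyses: "Two-tailed tests and an alpha level of .05 will be used". It adds that effect sizes will be looked at as well, because the sample is small.

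Other sections define the primary set differently. Primary Aim 1 in section 2 names cocaine urine, opioid urine, opioid craving and cocaine craving, but neither the all-negative screen nor cue reactivity. Section 7c gives the baseline-to-final-week comparison of cue reactivity under Primary Aim 1 and again under Secondary Aims 1 and 3.

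On the cue task itself, section 4a says of the baseline visit: "They may also complete a cue-induced craving paradigm". Of the final visit it says that "participants will complete a urine drug screen and self-report measures, and tasks", without naming which tasks.

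**The concern.** With several outcomes of equal standing, the plan does not say what the trial has shown if, for example, cocaine craving is significant and all the urine outcomes are null. Nor does it say whether the group term or the group-by-time term decides a given outcome. Those choices would then be made with the results in view. One nominally significant result among several null ones could be reported as a positive primary finding, at a false-positive risk well above the stated .05.

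The differing lists add to this. A reader holding section 2 and a reader holding section 7a would count different numbers of primary outcomes and could disagree about whether cue reactivity is one of them.

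**Working it through.** The plan states no familywise error rate, so there is no figure of its own to reproduce. The check asks how likely at least one p<.05 is if the drug does nothing.

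**Inputs from the documents.** Two-tailed .05 per test (7c); six or seven primary outcomes (7a); four in Aim 1 (section 2).

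**Assumptions.** One test per outcome, each with a true 5% error rate; jointly normal test statistics; correlations, none of which the documents give.

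**Step 1: independence.** 1 − 0.95^k gives:
- k = 4: 18.5%
- k = 6: 26.5%
- k = 7: 30.2%

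This overstates the risk, because the all-negative screen is partly built from the opioid and cocaine results. A simulation of that overlap assumed 20 per arm, 8 screens each and t-tests on each person's proportion of positive screens. The three urine outcomes together gave 10.5-12.7%, against 1 − 0.95^3 = 14.3%.

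**Step 2: block correlations.** P(any |z| > 1.96) was simulated with assumed correlations of 0.4-0.7 among urine outcomes, 0.5-0.8 among rating scales, and 0.2-0.4 between the two groups.

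| Urine / ratings / cross | Four (2+2) | Six (3+3) | Seven (3+4) |
|---|---|---|---|
| .4 / .5 / .2 | 17.3% | 23.6% | 26.1% |
| .55 / .65 / .3 | 16.2% | 21.3% | 23.3% |
| .7 / .8 / .4 | 14.6% | 18.5% | 19.8% |
| common 0.9 | 9.4% | 10.8% | 11.4% |

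Other plausible blocks widen the range for six or seven outcomes to about 17-29%.

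**Step 3: patient-level cross-check.** Simulating null trials at an assumed 20 per arm, with the negative screen derived from the opioid and cocaine results, gave 19-23% for six outcomes and 22-27% for seven.

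**Step 4: dependence on the success rule.** If instead every primary had to be significant, the same block settings give under 0.2% for four, six or seven outcomes, and about 1.4-1.9% at a common 0.9. If either the group or the interaction term could count for each outcome, there would be 12 or 14 tests. Under independence that gives 1 − 0.95^12 = 46% or 1 − 0.95^14 = 51%, again as an illustration only.

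**Step 5: cue reactivity.** Section 7a makes it primary and 7c compares it between baseline and the final week, while 4a makes the baseline task optional. A participant without the baseline task has no baseline-to-final change to contribute.

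**The case against.** The strongest reply is that the percentages depend on a rule the plan never states. A reader might infer that this trial has an 18-26% false-positive rate. The documents do not support that, because nothing says one significant primary is enough. Aim 1 in section 2 joins its outcomes with 'and', and if all were required the error would fall far below 5%. This objection stands, and the percentages must be read as conditional. It does not remove the gap: the plan does not state the all-required rule either, and section 1 words the urine hypothesis as cocaine and/or opioids.

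A second reply is that this is a pilot. Section 1 describes preliminary data, section 3 a proof of concept, and section 6c disclaims any intention to report to the FDA as a well-controlled study. A reader might infer from the placebo justification in 4f, or from the claim of sufficient power for all aims in 7c, that a lone p<.05 will be presented as proof of efficacy. Neither sentence is a decision rule, so that is conjecture. Pilot status limits the stakes. But looking at effect sizes in addition to tests at .05 does not say how mixed results are to be read.

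On the cue task, a reader might infer that 4a and 7a contradict each other outright. They do not: the statement in 7a names no visit, and 4a describes its measures in general as ones that may be used. The tension is between the optional baseline task and the baseline comparison in 7c. Nor would a participant without a baseline value necessarily be dropped, since a mixed model can still use the final-week rating. This is a missing-baseline question, separate from multiplicity.

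**Conclusion.** The concern holds in a limited form. Three gaps are plain from the text and need no assumption: no lead outcome, no deciding model term or rule for mixed results, and a primary set that differs between section 2, 7a and the two places in 7c.

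The size is conditional. If any one significant primary counted as success, the chance of a false positive would be about 18-26% for the six or seven outcomes in 7a and 15-17% for the four in Aim 1, under the assumed blocks. It would be about 9-11% at an assumed common 0.9. All of these exceed .05, but none is a bound or a property of the plan as written. In a 40-person pilot the severity is modest. The change is still worth making because it is cheap and has to be made before unblinding to be credible.

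The cue-task point is smaller and separate: a primary outcome compared with baseline rests on an optional baseline measurement.

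**What to change.** Before unblinding:

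1. Make sections 2, 7a and 7c agree on the primary set, including whether cue reactivity is primary or secondary and whether it is one outcome or two.
2. In 7a, name one lead primary outcome, tested at .05. Cocaine-positive urine is a candidate given the emphasis in section 3, but Aim 1 gives cocaine and opioids equal standing, so the choice belongs to the investigators.
3. In 7c, name the term, group or group-by-time, that decides it.
4. Report the other outcomes as secondary or exploratory, with estimates and 95% confidence intervals.

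Alternatively, state that all the primary analyses are exploratory and that no efficacy conclusion will rest on a single p<.05.

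For cue reactivity, either make the task standard at the baseline and final visits in 4a or reclassify the outcome as exploratory. If it becomes standard, check section 10, where visit payment depends on the tasks required and the maximum is $445.

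**Cost.** Wording changes and no added participants; a standard cue task would add one baseline task for those who would otherwise have skipped it. The lead outcome keeps the full .05. By contrast, Bonferroni over six or seven outcomes would test at .05/6 = .0083 or .05/7 = .0071. For an assumed standardised difference of 0.8 at an assumed 20 per arm, on a single between-group comparison, power would fall from 72% to 46% or 44%. The downside of a lead outcome is that the others become supportive only; under the exploratory option, the trial makes no confirmatory claim.
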